6.3.6 Concomitant Medications

At the entry and post-entry visits, record the new and discontinued medications in the source document and CRFs.

6.3.7 Adherence Assessments for cART and TB Medications

Adherence will be carefully assessed at screening, entry/day 0 and post entry visits using the ACTG self-report questionnaires completed by the participant or completed with the help of site staff (counselor- or nurse-driven). All participants will also have their TB treatment record reviewed to monitor adherence to treatment. Participants will be encouraged to maintain perfect adherence. Participants will be encouraged to bring documentation of TB treatment history, if available, TB medication, and cART at all study visits. For sites with clinics located at a different location from the TB and ARV clinic, study staff will be encouraged to work closely with TB and ARV providers for scheduling of participants, provision of medication, and monitoring of adherence to medication.

6.3.8 Laboratory Evaluations

At screening and entry all laboratory values must be recorded. For post-entry assessments, record all \geq Grade 3 laboratory values. All laboratory toxicities that led to a change in treatment, regardless of grade, must be recorded. Further evaluation will be required for those events that meet EAE or ICH reporting requirements. All protocol required labs will be done at the DAIDS-approved local lab unless otherwise specified.

Hematology

Perform hemoglobin, hematocrit, white blood cell count (WBC), absolute neutrophil count (ANC), and platelets as clinically indicated in addition to the visits specified in section 6.1.

Blood Chemistries

Perform electrolytes (sodium, potassium, chloride, and bicarbonate), creatinine, and blood urea nitrogen as clinically indicated in addition to the visits specified in section 6.1.

Liver Function Tests (LFTs)

Perform total bilirubin, AST (SGOT), and ALT (SGPT), albumin as clinically indicated in addition to the visits specified in section 6.1.

Pregnancy Test

At screening, serum or urine β -HCG (urine test must have a sensitivity of ≤ 25 mIU/mL) may be used.

Urine β -HCG may be used at the entry, post-entry, and premature study discontinuation visits and when clinically indicated.

There must be a negative pregnancy test within 30 days prior to study entry as well as at the time of study entry.

Perform as clinically indicated in addition to the visits specified in section 6.1.

Plasma Progesterone Levels

This will be done at a central lab. For details, please see the LPC found on the A5338 PSWP.

Serum FSH

At screening must be performed on women with LMP >35 days. For details, please see the current laboratory processing chart (LPC) found on the A5338 PSWP.

6.3.9 Immunologic Studies

CD4+/CD8+

Obtain CD4+ and CD8+ cell counts and percentages at study entry from a laboratory that possesses a CLIA certification or equivalent.

6.3.10 Virologic Studies

Plasma HIV-1 RNA

HIV-1 RNA must be performed by a laboratory certified by the DAIDS Virology Quality Assurance (VQA) Program at study entry and at week 12.

6.3.11 DMPA Injection

DMPA 150 mg will be administered intramuscularly (IM) as a single-dose at entry/week 0 after all blood samples for week 0 have been drawn.

Participants who successfully completed all their study requirements will be offered an extra dose of DMPA at no cost after all evaluations for the week 12 visit are completed, if in the opinion of the investigator the second DMPA dose does not present unnecessary risk to the participant. DMPA dose should be given after DMPA level and other blood work have been drawn.

6.3.12 Pharmacokinetic Assays

MPA Levels

Plasma will be obtained for MPA levels. For details, please see section 10.2 and the LPC found on the A5338 PSWP.

6.3.13 Whole Blood for Drug Metabolism Genotype

A single whole blood sample will be obtained at entry from all study participants for human genotyping of polymorphisms that have been associated with metabolism and/or transport of the study drugs, including EFV (eg, CYP2B6), RIF (eg, SLCO1B1), and DMPA. The samples will be processed at the Vanderbilt DNA Resources Core Laboratory. See the LPC on the A5338 PSWP for details regarding processing and shipping.

If at Entry/week 0 the whole blood for drug metabolism genotype it is not obtained, this sample may be obtained at any later visit week.

6.3.14 Metabolic Studies

Biomarkers of Bone Metabolism

Serum will be collected and stored for future studies of biomarkers of bone metabolism. For details, please see the LPC found on the A5338 PSWP.

7.0 CLINICAL MANAGEMENT ISSUES

7.1 Toxicity

Toxicities will be evaluated and managed by the study team in close consultation with the participants' primary care clinicians. Ongoing communication between the ACTG study staff and the participants' clinicians will be encouraged. If either the study team or primary care clinician becomes aware of an adverse event, he/she will contact the other within 24 hours of awareness.

For participants who experience toxicities that require treatment interruption or changes, a detailed letter with the results will be sent to primary care physicians by the study staff informing them about the toxicities and planned management from the study perspective.

If TB medication or cART is held for toxicity by the primary care physician, participants must inform the study team. Information about these treatment modification/interruptions must be recorded on the source document and CRF.

Grades 1 and 2: can be managed as per standard of care by the study doctor.

Vaginal Bleeding: \geq Grade 2 must be closely monitored and managed as per standard of care.

Grades 3 and 4: participants must be stabilized and referred immediately if required to obtain treatment at local hospital.

7.2 Pregnancy

If a participant becomes pregnant on study, she will continue to be followed on study and on cART and TB treatment, and have the study evaluations performed following the visit schedule in section 6.1, except the PK evaluation, until she completes the study. After she completes the study, she will be followed for safety until the outcome of her pregnancy is known.

If a woman has completed the study or chooses to discontinue from the study before the end of the pregnancy, then site staff should request permission to contact her regarding pregnancy outcomes at the end of pregnancy. If the information is obtained, pregnancy outcomes will be submitted on a CRF at the end of the pregnancy.

Pregnancy Outcomes and Reporting

A Pregnancy Outcomes CRF should be completed for all participants who become pregnant. The intrapartum complications and/or pregnancy outcome should be recorded on the CRFs.

Sites are encouraged to report prospectively any pregnancy to The Antiretroviral Pregnancy Registry if such occurs during this study. More information is available at www.apregistry.com; [contact] or [contact]; [contact].

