3.0 STUDY DESIGN

A5338 is an open-label, non-randomized 12-week, single-arm study to determine the PK of single-dose DMPA among women with TB and HIV co-infection who are receiving RIF-containing TB treatment plus EFV-based cART. Biomarkers of suppression of ovulation will also be evaluated. Participants will be HIV and TB co-infected women who have completed the intensive phase and are already in the continuation phase of RIF-containing TB treatment and who have been on EFV-based cART for at least 4 weeks.

Women diagnosed with TB and who are not already receiving HIV treatment at the time of screening for eligibility may start cART at any time between 2 and 8 weeks after TB treatment has been initiated, at the discretion of the treating physician and health care provider at the local clinic and in accordance with national and local treatment guidelines. Women who develop TB while on ART may also participate in the study. At study entry, all participants will receive a single IM injection of DMPA.

We will estimate individual MPA elimination rates, and then examine if any participant has a plasma progesterone level >5 ng/mL by the time that the estimated MPA level reaches 0.1 ng/mL. If data allows, a correlation between plasma progesterone levels and MPA concentrations observed at study weeks 10 and 12 will be investigated to better understand a minimum threshold of MPA concentration level to prevent ovulation using plasma progesterone level. If MPA clearance is induced by the co-administered drugs, the study week 10 and later are thought to be the times when ovulation would be most likely to occur, and increased plasma progesterone levels would be seen.

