The primary analysis outcome will be the proportion of women with sub-therapeutic MPA levels (<0.1 ng/mL) at 12 weeks. A one-sided binomial test with significance level 0.05 will be used to test the null hypothesis that the proportion of women with sub-therapeutic MPA level is 6% or less. A sample size of 42 women provides 90% power to reject the null hypothesis if the proportion of women with sub-therapeutic MPA levels in this study is at least 21% (this is 15% or higher increase from the 6% threshold). With a sample size of 42 women, the underlying true proportion will be declared as statistically significant increase if 6 or more women have sub-therapeutic MPA levels at 12 weeks (this is equivalent to saying that 90% CI for the underlying proportion is entirely above the 6% threshold). Based on the results from a PK study of oral contraceptives containing ethinyl estradiol (estrogen) and norethindrone (progestin) which are metabolized by CYP3A4 enzyme [58], the study team considers that the underlying proportion of women with sub-therapeutic MPA levels of 21% or higher (15% or higher

increase from the 6% threshold) is plausible in the setting of coadministration with EFV and RIF.

The statistical power was also examined to see if the sample size will achieve a plausible power to detect a clinically meaningful decrease (30%) in MPA concentration at 12 weeks (MPA C_{min}) as one of the secondary objectives. With a significance level of 0.05, a one-sided t-test showed about 91% and 84% power to detect a 30% decline when the coefficient of variation (CV) is 60% and 70%, respectively (in the ACTG study A5093, CV of MPA C_{min} was approximately 57% when coadministered with EFV). We note that this power was examined in \log_e -scale since it is known that PK parameter C_{min} has a \log -normal distribution.

To protect against 10% loss of the primary outcomes after study accrual is closed, the study will enroll a total of 46 women. (In the ACTG DMPA study, A5093, the loss of the primary outcomes of week 12 was 9.8% [6 of 61 participants] due to either sample specimen loss or assay results not available.)

A participant is considered to be evaluable for the primary objective if the participant completes the MPA PK sampling during the study period of 12 weeks after DMPA administration. The participant replacement criteria are described in sections 8.1 and 8.2.

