9.6 Analyses

A detailed statistical analysis plan will be developed after protocol Version 1.0 is finalized and before the study is open to accrual. The following will provide a summary of analyses that will state key analysis approaches.

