9.6.1 Analyses of Primary Outcome Measurements

The proportion of participants with sub-therapeutic MPA levels (<0.1 ng/mL) will be estimated based on the participants who complete the PK sampling at 12 weeks after DMPA administration. A 90% confidence interval (CI) will be provided for proportion using Clopper-Pearson exact method for binomial measurements. This CI will provide us reasonable evidence that the true proportion is greater than the threshold (6%), by determining whether the 90% CI is entirely above the threshold.

Individual-specific MPA concentration-time curves in the elimination phase will be estimated by fitting \log_e -linear regression models to the data of MPA concentrations obtained at time of maximum MPA concentration and later. These estimated individual elimination curves will then be used to estimate the times (weeks) where MPA concentration levels reach at 0.1 ng/mL. We will present descriptive statistics of these estimated weeks including mean, SD, median, interquartile range, minimum and maximum. Mixed-effects model analysis (allowing individual elimination slope to be both fixed and random variable) with repeated measurements within individual participants will also be performed to estimate the times for comparison purposes with the results obtained using the \log -linear regression models fitted for individual participants. These modeling approaches will provide the population mean estimate of the time where MPA concentration level reaches at 0.1 ng/mL with 90% CI, which will guide us to determine optimal dosing frequency of DMPA in the study population. Details of these modeling approaches will be described in the statistical analysis plan that will be generated separately and approved by study team.

Descriptive statistics of plasma progesterone levels will be tabulated by study week. If there are participants with progesterone levels >5 ng/mL, the proportion and percentage of participants with progesterone levels >5 ng/mL will be tabulated by study week.

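### Does stopping PK evaluation on pregnancy, with a primary proportion limited to women who have a week-12 MPA value, bias the primary result?

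*Protocol*

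**What the plan says.** Under Protocol section 7.2, a woman who becomes pregnant stays on study and is to "have the study evaluations performed following the visit schedule in section 6.1, except the PK evaluation, until she completes the study". A Pregnancy Outcomes CRF is completed for her.

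Section 9.4 sets evaluability: "A participant is considered to be evaluable for the primary objective if the participant completes the MPA PK sampling" over the 12 weeks. Section 9.6.1 says that the proportion with MPA below 0.1 ng/mL "will be estimated based on the participants who complete the PK sampling at 12 weeks after DMPA administration", with an exact 90% Clopper-Pearson interval compared with 6%. For 42 women, section 9.4 states that the true proportion "will be declared as statistically significant increase if 6 or more women have sub-therapeutic MPA levels at 12 weeks". Enrolment is 46, to allow for 10% loss.

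The schedule in section 6.1 has post-entry pregnancy tests at weeks 4 and 12. Section 6.3.8 adds that a urine test "may be used at the entry, post-entry, and premature study discontinuation visits and when clinically indicated". Section 3.0 expects that, if MPA clearance is induced, "the study week 10 and later are thought to be the times when ovulation would be most likely to occur".

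Section 9.6 is presented as a summary: "A detailed statistical analysis plan will be developed after protocol Version 1.0 is finalized and before the study is open to accrual". The supplied SAP covers only secondary objectives 1.3.1 and 1.3.2.

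**The concern.** In a contraception study, a rule that ends drug-level sampling at pregnancy looks like a way to lose the very women in whom the drug level fell too low. If low MPA leads to ovulation and pregnancy, and pregnancy leads to a missing week-12 value, the observed sub-therapeutic proportion is pulled down and the completers analysis favours the null hypothesis. Section 7.2 is also silent on whether a sample drawn at the week-12 visit is kept when pregnancy is first found at that visit.

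The decision rests on a small count, so one woman can matter at the boundary. Removing one sub-therapeutic woman from 6/42 leaves 5/41, and the lower limit falls from 6.41% to 4.93%. The supplied documents specify no imputation, bound or sensitivity analysis for women without a week-12 value, whatever the reason.

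**Working it through.** **The plan's own figures.** Exact binomial, null 6%, alternative 21%, n = 42 (section 9.4):

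- P(X ≥ 6 | 42, 0.06) = 0.0382; P(X ≥ 5 | 42, 0.06) = 0.1052. Six is the right critical count.
- P(X ≥ 6 | 42, 0.21) = 0.901, matching the stated 90% power.
- The Clopper-Pearson 90% lower limit for 6/42 is 6.41%, above 6%, as the protocol says.

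**Expected pregnancies.** Inputs: 46 enrolled, 12 weeks, 0.3% per year (section 9.4, correct use).

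46 × (12/52) × 0.003 = 0.032.

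**Chance that a lost pregnancy reverses the decision.** The completers must sit one short, at 5/42. Adding one sub-therapeutic woman gives 6/43, with P(X ≥ 6 | 43, 0.06) = 0.0422, which is declared. Multiplying P(X = 5 | 42) by 0.032:

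| True rate (assumed) | P(X = 5 of 42) | × 0.032 |
|---|---|---|
| 6% | 0.067 | 0.0021 |
| 12% | 0.187 | 0.0060 |
| 15% | 0.158 | 0.0050 |
| 21% | 0.057 | 0.0018 |

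These are ceilings for that pregnancy rate. The pregnancy must also be recognised before the week-12 sample, and the woman's week-12 MPA must truly be below 0.1 ng/mL.

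**How narrow the route is.** The only scheduled test after entry and before week 12 is at week 4. A pregnancy found then began near entry. Section 2.1.1 puts peak MPA (1 to 7 ng/mL) within 3 weeks of injection, so a positive week-4 test says little about induced clearance at week 12. Pregnancies from ovulation at week 10 or later would mostly surface at or after week 12, when the PK sample is due at the same visit. What remains is a clinically indicated test between visits, in women whom section 4.1.8 requires to use additional contraception if pregnancy is possible.

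**Losses of any cause.** Assume 42 of 46 have a week-12 value. The critical count is 6 for n = 34 to 44 and 7 for n = 45 to 56: P(X ≥ 6 | 44) = 0.0465, P(X ≥ 6 | 45) = 0.0510 and P(X ≥ 7 | 46) = 0.0190 at 6%. Best- and worst-case completions to 46 therefore disagree when 3 to 6 completers are sub-therapeutic. Those are extremes: all four missing women being sub-therapeutic has probability 0.12⁴ = 0.0002 at a true 12%, and 0.21⁴ = 0.0019 at 21%.

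Under purely random loss, let X ~ Bin(42, p) and Y ~ Bin(4, p), and compare X ≥ 6 with X + Y ≥ 7:

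| True rate (assumed) | Decisions differ | Of which X = 6, Y = 0 |
|---|---|---|
| 6% | 0.022 | 0.021 |
| 12% | 0.109 | 0.094 |
| 15% | 0.109 | 0.090 |
| 21% | 0.048 | 0.036 |

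Most of the disagreement is 6/42 being declared while 6/46 is not. That comes from the step in the critical count between n = 44 and n = 45. It is a property of an exact test on a small count, not bias from missing data.

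**The case for a change.** The strongest case for a change has three parts.

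First, the 0.3% rate is for ordinary DMPA use, whereas the study hypothesis in section 1.1 is that RIF and EFV reduce efficacy. That stands. A ten-fold rate, taken as an assumption, gives about 0.3 expected pregnancies and a ceiling of about 6% at a true 12%, before the further conditions above. The route stays minor.

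Second, with four women missing, the extreme-case bounds would disagree often: P(3 ≤ X ≤ 6 | 42) is 0.66 at a true 12%. That is correct arithmetic, but bounds so wide would rarely settle anything. Nor is there evidence that the anticipated losses depend on MPA. The 9.8% loss in the earlier study that supports the 10% allowance was "due to either sample specimen loss or assay results not available".

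Third, the remedy appears cheap: keep sampling pregnant women, and predict week-12 MPA for everyone else who lacks it. Neither part is clean. New research sampling in pregnancy would need an amendment with IRB/EC approval, and MPA measured in pregnancy would need its own caveat. Predicting for all women without a value would include those replaced under section 8.2 for stopping RIF or substituting EFV. Their earlier slopes would be extrapolated to a regimen they no longer took, while objective 1.2.1 concerns women taking both.

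What survives is that section 7.2 does not say what happens to a week-12 sample when pregnancy is first detected at that visit, and that the supplied text lists no sensitivity analysis for missing week-12 values.

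**Conclusion.** The passages do combine as described, but the plan does not need to change. The pregnancy rule has about 0.03 expected occurrences and at most about a 0.6% chance of bearing on the decision, given the protocol's 0.3% yearly rate, 46 women and true sub-therapeutic rates between 6% and 21%. Pregnancy is not the primary endpoint and does not prove MPA below 0.1 ng/mL. The event is not hidden either: the woman stays in follow-up, her progesterone levels remain scheduled as a primary outcome measure, her pregnancy is reported, and under Letter of Amendment #1 two or more pregnancies are a trigger for independent committee review.

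The missing sensitivity analysis is detail not given in a section that announces itself as a summary. The supplied SAP is confined to two secondary objectives, so a separate plan for the primary analysis cannot be ruled out. Other provisions already limit or use incomplete data. Missing the week-10 or week-12 visit leads to discontinuation and replacement under section 8.1. Letter of Amendment #1 adds regular review of data availability. Earlier samples can enter the elimination fits in section 9.6.1 and the population model in section 10.3.

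The rest is ordinary analyst practice: analyse a week-12 sample already drawn, report how many week-12 values are missing and why, and compute the exact interval at the actual n. The interval rule in section 9.6.1 already works for any n; only the count of six is tied to 42.

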7.3 Breastfeeding

Sites should follow local guidelines to prevent Mother-to-Child Transmission (MTCT) during breastfeeding.

8.0 CRITERIA FOR PREMATURE STUDY DISCONTINUATION

8.1 Participant meets one or more of the criteria for noncompliance.

8.1.1 Failure by the participant to attend 2 consecutive visits at week 2, 4, 6, or 8.

8.1.2 Failure by the participant to attend any of the week 10 or week 12 visit.

8.1.3 Missed 2 or more of the RIF and EFV doses within one week prior to PK sampling at week 2, 4, 6, or 8 and did not return with acceptable adherence (ie, missed 2 or more of the RIF and EFV doses) for the rescheduled PK sampling for 2 consecutive study weeks.

8.1.4 Missed 2 or more of the RIF and EFV doses within one week prior to PK sampling at week 10 or 12 and did not return with acceptable adherence (ie, missed 2 or more of the RIF and EFV doses) for the rescheduled PK sampling.

NOTE: A participant who prematurely discontinues from the study due to noncompliance will be replaced.

8.2 Participant requires a change in the cART or TB regimen during the 12 weeks on study.

8.2.1 For the purposes of this study, a cART change that will warrant replacement of the participant includes:

- Addition of another NNRTI or a PI resulting in a NNRTI/PI or any PI combination therapy.
- Any substitution within the NNRTI class.
- Addition of an integrase inhibitor or entry inhibitor to the regimen.

NOTE: Participants may stay on study if they change or discontinue one or more of their NRTIs since this class of medications is not thought to affect the metabolism of DMPA or EFV. See section 5.4.2 for the NRTI combinations that are not allowed in this study.

8.2.2 For the purposes of this study, a TB regimen change that will warrant replacement of the participant includes:

- Stopping RIF secondary to toxicity or resistance.
- Addition of other TB medications to the study TB regimen of RIF and INH.

8.3 Request by the participant to withdraw.

- 8.4 Request of the primary care provider if s/he thinks the study is no longer in the best interest of the participant.
- 8.5 Participant judged by the investigator to be at significant risk of failing to comply with the provisions of the protocol as to cause harm to self or seriously interfere with the validity of the study results.
- 8.6 At the discretion of the IRB/Ethics Committee, NIAID, Office for Human Research Protections (OHRP), other government agencies as part of their duties, or investigator.

